### **3.3.2. Protocol deviations**

The fraction of eligible censused children who accept the intervention will be reported. Communities for which this fraction falls below 60% at a specific census will be tabulated and reported.

In addition, if the fraction of children identified on a subsequent census falls below 75%, an investigation will be conducted. The number of such communities will be tabulated and reported, and sensitivity analyses omitting such communities will be reported.

Formal protocol deviations of two types are noted: (1) individual-level deviation, in which an ineligible individual is mistakenly treated, and (2) community-level deviation, in which a community is mistakenly treated with the wrong intervention. Any such events will be tabulated and reported. Note that any community which receives the wrong treatment will be analyzed according to the original randomization assignment (intention to treat).

### **3.3.3. Analysis Populations**

Community-level data will be analyzed on an intention-to-treat basis, covering all inter-census intervals for which follow-up data are available. The random sample of communities selected for the AMR substudy will contribute to the mortality analyses.

Since AVENIR will randomize grappes before formal enrollment at baseline, the trial will analyze only grappes that are enrolled at baseline according to their assigned treatment. Grappes that are randomized but do not meet the trial's enrollment criteria will not be included in the analysis.

Modified per protocol analyses will be conducted that exclude communities with below 60% antibiotic coverage in the targeted age group. The number of such communities and their mean coverage will be reported, and such analyses will be sharply distinguished from the prespecified primary and secondary analyses.

## 3.4. Trial Population

### 3.4.1. Screening data

AVENIR will report the number of communities screened by region and the reasons communities were not enrolled based on eligibility criteria described in the next section.

### 3.4.2. Eligibility

This information repeats Protocol v10 section 4.3 Eligibility - Intervention.

#### At the community-level, eligibility includes:

##### *Inclusion Criteria:*

- Location in Dosso, Tahoua, Maradi, Zinder, or Tillabéri regions
- Population 250 to 2,499\*
- Distance > 5 km from district headquarters town
- Verbal consent of community leader(s)

##### *Exclusion criteria:*

- Inaccessible or unsafe for study team
- “Quartier” designation on national census

\*Population size as estimated from the most recent national census or projections

#### At the individual-level, eligibility includes:

##### *Inclusion criteria:*

- Age 1-59 months
- Primary residence in a study community
- Verbal consent of caregiver/guardian for study participation
- Weight  $\geq 3.0$  kg

##### *Exclusion criteria:*

- Known allergy to macrolides

### 3.4.3. Recruitment

The CONSORT flow diagram will follow the model of the MORDOR I trial [2] and will include a tabulation of the number of (a) available communities, (b) eligible communities, and (c) enrolled communities by arm.

### 3.4.4. Withdrawal/follow-up

Additional information will be provided. Specifically, (d) average number of individuals per community, (e) coverage and number of treatments given, and (f) number of individuals for whom end of intercensus mortality data are available.

As a large simple trial, AVENIR will not collect information regarding the specific reasons or timing for any loss to follow-up at the individual level.

### **3.4.5. Baseline patient characteristics**

Since AVENIR is a large simple trial it will not collect extensive information about individual participants. We propose to summarize the community size (number of eligible children), child age distribution, and percentage female for enrolled communities.

## **3.5. Analysis**

### **3.5.1. Outcome definitions**

#### **Mortality Trial Primary Outcomes**

The trial has three primary outcomes, each a different comparison of the mortality rate (deaths per 1,000 persons at risk) at 2.5 years from the first child enrolled, with a window of 3 months.

- Mortality rate (deaths per 1,000 person-years at risk) among children 1-59 months of age compared between communities that receive azithromycin delivered to children ages 1-59 months and communities that receive placebo at 2.5 years
- Mortality rate (deaths per 1,000 person-years at risk) among children 1-11 months of age compared between communities that receive azithromycin delivered only to children ages 1-11 months and communities that receive placebo at 2.5 years
- Mortality rate (deaths per 1,000 person-years at risk) among children 12-59 months of age compared between communities that receive azithromycin delivered to children ages 1-11 months and communities that receive azithromycin delivered to children ages 1-59 months at 2.5 years

Mortality will be monitored through biannual census data collection. Trained census workers will use a custom-designed mobile application on smartphones to conduct the census. Census workers will visit each household in assigned study communities to obtain household consent for participation, and to collect demographic data on the head of household, all mothers in the household, and all children 1-59 months in the household. For eligible children, dose will be determined via weight or height and administered by the census worker. At subsequent census periods, the census workers return to each household and update the vital status of all children, indicating whether a child is alive, has died, has moved, or has an unknown status. New children and households will be added.

A child will be included as a death in the primary outcome analysis if they are present on one census and absent on the subsequent census due to death (inter-census interval). Person-time at risk will be calculated as time alive and eligible for treatment while living in the study area, with children who died contributing half of the person-time for their last inter-census interval. Children who moved, have an unknown status, or are missing from one census will contribute no person-time.

If the study team fails to measure a community for a single census due to security or logistical reasons, but re-visits the community in the following census, then person-time and outcomes for the 1-year period (2 inter-census intervals) will be counted toward the primary outcome. In this case, as with the 6-month inter-census interval, person-time at risk will be calculated as time alive and eligible for treatment for the double inter-census interval

(approximately 12 months), and children who moved, have an unknown status, or are missing from one census contributing no person-time. Children who died will contribute half of the person-time between the first census date of the double inter-census interval and their death date. Death date will be used to determine to which inter-census interval the death will belong.

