#### ***Mortality primary outcomes***

*Mortality primary outcome 1:* mortality in 1-59 month olds, assessed at 2.5 years (based on at most 2 years of follow-up per community), comparing the 1-59 month and the placebo arms. Assuming a standard deviation of approximately 0.023, we find that 1,116 communities per arm will provide approximately 80% power to detect a 10% relative reduction, assuming a baseline mortality rate of 27 per thousand person-years among children 1-59 months old and an alpha of 0.05. The absolute effect size is a mortality rate difference of 2.7 deaths per 1000 person-years. This calculation is based on the standard Z-test formula for power (treating the mortality rate in each community as a continuous variable). The calculation does not involve a correction for multiple comparisons since the analysis uses a hierarchical testing approach for the three mortality outcomes, as described below.

*Mortality primary outcome 2:* mortality in 1-11 month olds, assessed at 2.5 years (based on at most 2 years of follow-up per community), comparing the 1-11 month arm and the placebo arm. Assuming a standard deviation of approximately 0.074, we find that 1,116 communities per arm will provide approximately 80% power to detect a 19% relative reduction, assuming a baseline

mortality rate of 45 deaths per thousand person-years among children 1-11 months old and an alpha of 0.05. The absolute effect size is a mortality rate difference of 8.8 per 1000 person-years. This calculation is based on the standard Z-test formula for power (treating the mortality rate in each community as a continuous variable). The calculation does not involve a correction for multiple comparisons since the analysis uses a hierarchical testing approach for the three mortality outcomes, as described below.

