### 3.5.2. Analysis methods

#### Mortality in the mortality/resistance trial

Our parameter of interest for comparisons of mortality between arms is the relative reduction in mortality measured by the incidence rate ratio (IRR). The primary analysis will be a Poisson regression that includes the count of deaths as the outcome and the community-level person-time at risk as an offset, with observations for each community's inter-census interval. The model will include an indicator variable for each active treatment arm. The adaptive allocation will be accounted for using pooled regression, including in the model additional indicator variables for each of three allocations in the trial (the initial, equal allocation plus 2 adaptations). For community  $i$  and randomization  $j$  ( $j = 1, 2, 3$ ), the model will be:

$$\log(Y_{ij}) - \log(T_{ij}) = \alpha + \beta A_{ij} + \sum_{j=2}^3 \gamma_j P_j,$$

where  $Y_{ij}$  is the number of deaths and  $T_{ij}$  is the person-time at risk in that community;  $A_{ij}$  is a treatment indicator that will vary by each comparison (details below), and  $P_j$  is an indicator for the two adaptive random allocations (the first equal allocation is the omitted category). We will

estimate 95% confidence intervals for the IRRs using bootstrap resampling (10,000 replicates) that resamples communities with replacement and re-estimates the IRRs.

For primary outcome 1 that compares mortality among 1-59 month olds, we will include in the analysis children ages 1-59 months in the 1-59 month treatment arm and placebo arm.  $A_{ij}$  will be an indicator of allocation to the 1-59 month treatment arm, and  $\exp(\hat{\beta})$  will estimate the IRR.

For primary outcome 2 that compares mortality among children ages 1-11 months, we will subset the analysis to children ages 1-11 months enrolled in the 1-11 month treatment arm and placebo arm.  $A_{ij}$  will be an indicator of allocation to the 1-11 month treatment arm, and  $\exp(\hat{\beta})$  will estimate the IRR.

Similarly, for primary outcome 3 that compares mortality among children ages 12-59 months, we will subset the analysis to children ages 12-59 month in the 1-11 month treatment arm and 1-59 month treatment arm.  $A_{ij}$  will be an indicator of allocation to the 1-59 month treatment arm, and  $\exp(\hat{\beta})$  will estimate the IRR.

Secondary mortality analyses will be estimated similarly from the model subset to the appropriate age range.

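### For double inter-census intervals the SAP credits a child who died with only half the time to the death date, which understates person-time in the primary mortality rate

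*SAP*

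**What the plan says.** SAP section 3.5.1 (Mortality Trial Primary Outcomes) has two rules for the person-time of a child who died.

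- **Ordinary six-month interval.** Person-time is time alive, eligible and resident, "with children who died contributing half of the person-time for their last inter-census interval". No death date is needed.
- **Double interval**, when a community misses one census and is visited at the next. The whole period enters the primary analysis: "then person-time and outcomes for the 1-year period (2 inter-census intervals) will be counted toward the primary outcome". The general definition is kept: "person-time at risk will be calculated as time alive and eligible for treatment for the double inter-census interval". For deaths the rule becomes: "Children who died will contribute half of the person-time between the first census date of the double inter-census interval and their death date". The next sentence uses the same date again: "Death date will be used to determine to which inter-census interval the death will belong".

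SAP section 3.5.2 then models the "count of deaths as the outcome and the community-level person-time at risk as an offset", with one observation per community and inter-census interval.

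**The concern.** Crediting half an interval is the usual approximation when all that is known is that a death fell somewhere inside it. Once the time is cut off at the death date, nothing is left to approximate, because the child was at risk for all of it. Halving it again removes person-time that was actually lived.

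The rule therefore conflicts with the definition given for double intervals in the same paragraph, and it differs from the single-interval rule it is meant to extend. Because person-time is the model offset, mortality rates in communities with a missed census are biased upward relative to other communities. The bias grows with mortality, so it is slightly larger in the arm with more deaths and pushes the rate ratio a little away from 1.

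**Working it through.** **The plan's own figure.** The documents give no person-time total to reproduce. The nearest stated figure is the power for primary outcome 1 in SAP 3.2.3: "Assuming a standard deviation of approximately 0.023, we find that 1,116 communities per arm will provide approximately 80% power", for a difference of 2.7 per 1,000 person-years at two-sided 0.05. The Z-test gives 0.0027 / (0.023 × √(2/1116)) − 1.96 = 2.773 − 1.960 = 0.813, so power is 0.792. This agrees with the SAP, and its planning rates are used below.

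**Individual deaths.** Months credited over 12 months from the opening census:

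| Death at month | Time actually alive | Six-month rule, mid-year census done | Double-interval rule |
|---|---|---|---|
| 4 | 4 | 3 | 2 |
| 11 | 11 | 6 + 3 = 9 | 5.5 |
| Mean, deaths uniform | 6 | (3 + 9)/2 = 6 | 3 |

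The six-month rule is right on average; the double-interval rule gives half. The death at month 11 also belongs, by its date, to the second interval. Yet its 5.5 months do not cover the first six months, which the child survived. The same holds for every second-interval death before month 12.

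**Total person-time, deaths uniform.** Take a one-year double interval and treat the planning rate r as the one-year risk. Correct person-time per child is (1 − r) + 0.50r; the SAP rule gives (1 − r) + 0.25r.

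- r = 0.027 (1–59 months): 0.97975 / 0.98650 − 1 = −0.68%
- r = 0.045 (1–11 months): 0.96625 / 0.97750 − 1 = −1.15%

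With a true ratio of 0.90, the treated-arm factors are 0.981775 / 0.987850 = 0.99385 at r = 0.0243, and 0.969625 / 0.979750 = 0.98967 at r = 0.0405. The rate ratio is multiplied by 0.99316 / 0.99385 (−0.07%) and by 0.98849 / 0.98967 (−0.12%).

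**Check with a constant hazard.** For hazard λ over one year, D = 1 − exp(−λ) die and S = exp(−λ) is the survivors' time. Exact person-time is D/λ, and the SAP rule gives S + (D/λ − S)/2. At λ = 0.027 these are 0.98662 and 0.97999, a shortfall of 0.67%. The ratios in the last column use the relative reductions in SAP 3.2.3 (10%, 19%, 11%) and treat every interval as double.

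| True rate per 1,000 | Person-time error | Rate under the SAP rule | True ratio → ratio under the rule |
|---|---|---|---|
| 27 | −0.67% | 27.18 | 0.900 → 0.8994 |
| 45 | −1.12% | 45.51 | 0.810 → 0.8083 |
| 24 | −0.60% | 24.14 | 0.890 → 0.8894 |

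Half of the 12-month interval, the simple midpoint rule, would give 26.998 for a true 27, so it is almost unbiased.

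**Share of double intervals.** This is not given. If they hold an assumed 5%, 10%, 25% or 100% of person-time in both arms, a true 27 becomes 27.01, 27.02, 27.05 or 27.18. If they held 10% in the active arm and none in placebo, a true ratio of 0.900 would become 0.9005.

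**The case against.** The strongest reply is that this cannot matter to the result. The parameter of interest is the rate ratio. Suppose the stated 80% power holds for a 10% reduction (19% in infants). The standard error of the log ratio is then about 0.105/2.8 = 0.038 (0.211/2.8 = 0.075). Even with every interval double, the shift is only about 0.02 to 0.03 standard errors. The rule is the same in every arm of a masked trial, and the P-values come from permuting labels with outcomes held fixed, so type I error is not threatened. All of this stands, and it is why the point is minor.

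Three further objections stand in part.

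- **Quality of the date.** Protocol section 4.4.8.2 lists only vital status at each census, not a date of death. A date good enough to choose between two six-month intervals may be too rough for exact person-time. That supports a fallback rule. It does not support halving the time to death.
- **Another repair exists.** One could credit half of the six-month interval in which the death falls, plus any earlier full interval. This is closer to the ordinary rule and also nearly unbiased. Either repair is acceptable, and the SAP should state one.
- **Late change.** The person-time wording was revised in SAP version 13 (October 2022), and the current version 16 dates from September 2024. A change to a primary-outcome definition at this stage needs a dated justification.

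None of these defends the sentence as written.

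**Conclusion.** The concern holds. Followed literally, the rule gives a wrong denominator in double intervals, and nothing else in the documents corrects or explains it. The direction is certain: half the time to death is always less than the time alive. Under uniform deaths the understatement of person-time within those intervals is 0.68% at 27 per 1,000 and 1.15% at 45 per 1,000. The rate ratio moves by about 0.1% for a true 10% reduction, and by about 0.2% for the 19% reduction planned in infants (0.8083/0.810).

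These sizes assume a 12-month double interval, complete follow-up, and no child ageing in or out of eligibility. The trial-wide effect depends on how many double intervals occur, which the documents do not say. This is a definition to correct. It affects reported absolute rates more than the ratio and does not threaten the primary conclusion or the power.

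**What to change.** Replace the sentence in SAP 3.5.1 with: *A child who died contributes all person-time from the opening census of the double interval up to the date of death; if that date is missing, the child contributes half of the double interval.* Where the double interval is split into two model rows, divide this time between the rows at the same boundary used to place the death.

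The cost is one sentence and a dated entry in the revision history. The analysis code should be checked against it. If offsets have already been computed under the literal rule, recompute them for the affected community intervals only. No new data are needed, since the SAP already relies on the death date.

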## Mortality Trial Secondary Outcomes

Two secondary outcomes include mortality rate comparisons at 2.5 years ( $\pm 3$  months) from the first child enrolled for the remaining comparisons between different age groups and arms

- Mortality rate (deaths per 1,000 person-years at risk) among children ages 12-59 months, with rates compared between communities that receive azithromycin delivered only to children ages 1-11 months and communities that receive placebo
- Mortality rate (deaths per 1,000 person-years at risk) among children ages 1-11 months, with rates compared between communities that receive azithromycin delivered only to children ages 1-11 months and communities that receive azithromycin delivered to children ages 1-59 months

## Antimicrobial Resistance Substudy Primary Outcomes

The trial will have two primary outcomes for antimicrobial resistance (AMR):

- Prevalence of genetic determinants of resistance to macrolides including those determinants known to be found in *Streptococcus pneumoniae*, *Streptococcus pyogenes*, and *Staphylococcus aureus* from nasopharyngeal swabs in children 1-59 months old at 24 months from baseline
- Load of genetic determinants of resistance to macrolides including those determinants known to be found in *Campylobacter*, *Salmonella* spp., *Shigella* spp., and *Escherichia coli* from rectal swabs in children 1-59 months old after 2 years of distributions

## Antimicrobial Resistance Substudy Secondary Outcomes

- Prevalence of genetic determinants of resistance to macrolides from nasopharyngeal swabs collected from children 7-12 years old after 2 years of distributions
- Prevalence of genetic determinants of resistance to macrolides from nasopharyngeal swabs collected from caregivers/guardians of eligible children after 2 years of distributions
- Prevalence of genetic determinants of resistance to other antibiotic classes in all swabs and samples listed above
- Proportion of macrolide resistant pneumococcal isolates from nasopharyngeal swabs collected from children 1-59 months
- Load of genetic determinants of resistance to all antibiotic classes from **stool samples** in caregivers/guardians of eligible children after 2 years of distributions

## Microbiome Substudy Outcomes.

Nasopharyngeal samples will be collected from children 1-59 months of age, children 7-12 years of age, and caregivers/guardians of children 1-59 months of age as described above and in the protocol. Rectal swabs will be collected from children 1-59 months of age and stool samples will be collected from caregivers of these children as described above and in the protocol. Each age group and sample type will be used to assess the following outcomes:

- Overall microbial structure after 2 years of distribution using Manhattan distance, adjusted for baseline and analyzed with PERMANOVA to compare by arm. Euclidean distance will be used in a secondary analysis.
- Shannon's diversity index (expressed as effective number) of the microbiome after 2 years of distribution, analyzed in a linear model with a covariate for arm and baseline numbers. Simpson's index (expressed as effective number) will be used in a secondary analysis.
- Relative abundance of individual microbial taxa at the genus and species level after 2 years of distribution, adjusted for baseline and analyzed with DESeq2 to compare by arm with a Benjamini-Hochberg correction to account for the number of comparisons using a false discovery rate of 5%.

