4.4.5.2. Sample Collections

150 of the communities in the Mortality Trial in the Dosso region will be randomly selected to be followed to monitor antimicrobial resistance. In each community, 30 children aged 1–59 months, 30 children 7–12 years, and 30 caregivers/guardians of eligible children will be randomly selected for sample collections at baseline and after 4 distributions. Samples will be collected in a random subset of 60 communities at baseline, and in all 150 AMR communities after 4 rounds (approximately 2 years).

An additional 40 communities that participated in the MORDOR 54 trial will be randomly selected for inclusion in sample collections at baseline. Of these 40 communities, 20 will be randomly selected from among those who received 5 rounds of azithromycin during MORDOR, and the other 20 communities be randomly selected from among those who received 3 rounds of azithromycin and 2 rounds of placebo during MORDOR. In each community, 30 children 1–59 months will be randomly selected to receive a rectal swab.

Furthermore, 60 communities whose children aged 1–59 months have received ~11 biannual

distributions of azithromycin (as opposed to placebo) during the MORDOR trial will be selected randomly: 20 randomized in AVENIR to two more years of biannual azithromycin to 1-59 month olds, 20 randomized to biannual azithromycin to 1-11 month olds, and 20 randomized to biannual placebo. 40 children per grappe, aged 1-59 months, will be randomly selected from the prior census. Examiners will perform a nasopharyngeal swab on each child, stored in STGG media.

In all communities selected for sample collections, treatment distribution for that round will be conducted after sample collections.

Refer to SAP for details of power calculations.

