4.4.8.3. Measurement of Sample Based Outcomes

In the Mortality and Resistance Trial, 150 AMR communities from the Dosso region will be randomly selected from the pool of eligible communities and followed to monitor antimicrobial resistance. Samples will be collected in a random subset of communities at baseline and in all 150 AMR communities after 2 years of distributions. For primary outcomes, samples will be processed from a subset of 150 communities.

In each of the selected Mortality/Resistance Trial communities, 30 children aged 1–59 months,

30 children aged 7–12 years, and 30 caregivers/guardians of eligible children will be randomly selected for additional monitoring. Nasopharyngeal samples will be collected from all sampled individuals. From children aged 1–59 months, rectal swabs, RDT, and dried blood spots will also be collected. In the sample of children aged 1–59 months, 10 children will be randomly selected for an additional nasopharyngeal swab which will be used for phenotypic testing. Samples will be collected at baseline and after 2 years of distributions.

To randomly select individuals for population-based monitoring in the Mortality/Resistance Trial, census data will be used. In the 150 Dosso communities selected for additional monitoring, the baseline and 24-month census will be separate from treatment and will include data collection on children aged 7–12 years old. The random samples of children in both age groups and caregivers/guardians will be selected from the census. To ensure that samples are collected on 30 individuals in each group, 50 children in both age groups and 50 caregivers/guardians will be randomly selected from the census data.

60 previously untreated communities will be incorporated into the Mortality/Resistance Trial in Round 4 and will receive rectal swab baseline collections. This is to account for rectal swab baseline samples collected in Round 1 that were damaged and unusable. 1 rectal swab will be collected from 30 children aged 1–59 months per community. Samples from community latrines and chicken feces will also be collected when available from the homes of the 30 children selected for this sample collection.

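### The microbiome analyses adjust for baseline, but at most 60 of the 150 resistance communities can supply one (possibly none for rectal swabs), and the SAP gives no rule for the rest

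*SAP*

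**What the plan says.** The SAP (3.5.1, Microbiome Substudy Outcomes) applies three analyses to each age group and sample type, and all three use baseline:

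- Overall structure is "adjusted for baseline and analyzed with PERMANOVA to compare by arm".
- Shannon diversity is "analyzed in a linear model with a covariate for arm and baseline numbers".
- Relative abundance of taxa is "adjusted for baseline and analyzed with DESeq2 to compare by arm".

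The protocol (4.4.5.2) sets the sampling: "Samples will be collected in a random subset of 60 communities at baseline, and in all 150 AMR communities after 4 rounds". A sentence just before it reads as if every community is sampled at both times, but 4.4.8.3 also limits baseline collection to a random subset.

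For rectal swabs, Protocol 4.4.8.3 adds: "60 previously untreated communities will be incorporated into the Mortality/Resistance Trial in Round 4 and will receive rectal swab baseline collections". The reason follows: "This is to account for rectal swab baseline samples collected in Round 1 that were damaged and unusable". The number of swabs lost is not given. Nasopharyngeal baseline samples are not reported as lost.

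The SAP's missing-data section (3.5.3) deals with mortality person-time and community drop-out. It says nothing about a missing baseline covariate. The protocol's own list of microbiome outcomes (4.4.4.2) does not mention baseline adjustment.

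**The concern.** A linear model with a baseline covariate needs a baseline value for every unit it analyses. At least 90 of the 150 communities sampled at 24 months have none by design, and the rectal baseline may be missing altogether. The Round 4 replacement swabs do not repair this. They come from communities not treated before Round 4, so these cannot be communities treated since Round 1, and no 24-month sampling of them is described.

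If the stated model is followed with ordinary software defaults, most 24-month microbiome data drop out of the diversity analysis, and the rectal version may not be possible to fit. If it is not followed, the set of communities and the form of adjustment will be chosen after the data are in hand. Both are avoidable for listed secondary outcomes.

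**Working it through.** The documents give no sample size or power for the microbiome outcomes, so there is no stated figure to reproduce. The nearest is AMR primary outcome 1 (SAP 3.2.3): 50 communities per arm, 30 specimens each, ICC 0.045, 30% against 38%, alpha 0.025. Effective n per arm = 1,500/(1 + 29 × 0.045) = 650.8, which gives power of 0.79 against the stated level of at least 80%. The inputs are therefore being read as intended.

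**Communities with a paired baseline, out of 150**

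- Nasopharyngeal: at most 60 (40%). A complete-case model drops 90/150 = 60%.
- Rectal: between 0 and 60, depending on how many Round 1 swabs survived. A complete-case model drops 60% to 100%.
- The 60 Round 4 communities add no pair.

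**Precision with 60 communities instead of 150**

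Assume the 60 split evenly, 20 per arm against 50.

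- Ratio of standard errors with no gain from adjustment: sqrt(50/20) = 1.58.
- The samples are drawn afresh from the census at each time point, so pairing is mainly at community level. If different children are sampled and community effects are perfectly stable, the largest correlation between baseline and follow-up community means is r = m × ICC/(1 + (m − 1) × ICC), with m = 30.
- ICC 0.045 (nasopharyngeal resistance): r = 1.35/2.305 = 0.59. Adjustment multiplies the standard error by sqrt(1 − r²) = 0.81, and 1.58 × 0.81 = 1.28.
- ICC 0.02 (rectal resistance load): r = 0.60/1.58 = 0.38. The multiplier is 0.925, and 1.58 × 0.925 = 1.46.
- For 60 adjusted communities to match 150 unadjusted ones, r must be at least sqrt(1 − 20/50) = 0.775, above both values.

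**Detectable difference** (80% power, two-sided alpha 0.05, in community-level SDs): (1.96 + 0.84) × sqrt((2/k) × (1 − r²)), with k communities per arm.

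| Analysis | k | r | Detectable difference |
|---|---|---|---|
| 150 communities, unadjusted | 50 | – | 0.56 |
| 60 communities, no baseline correlation | 20 | 0 | 0.89 |
| 60 communities, adjusted | 20 | 0.38 | 0.82 |
| 60 communities, adjusted | 20 | 0.59 | 0.72 |

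These figures take 60 communities as retained. With fewer surviving rectal baselines the loss is larger, and with none the model cannot be fitted.

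**If the analysis is limited to the 60 baseline communities**

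The nasopharyngeal model then loses none of its 60, but 90 communities with 24-month samples go unused. The rectal model still lacks whatever baselines were damaged.

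**The case against.** Several points on the other side have force.

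- The SAP does not say that communities without a baseline are dropped. Complete-case fitting follows directly only for the linear diversity model, and only if no missing-data method is used. For PERMANOVA and DESeq2 the form of adjustment is undefined. An unpaired arm-by-time design would keep every sample and could use the Round 4 swabs as an unpaired reference. This stands, so the loss cannot be attributed to all three analyses.
- The SAP never gives 150 as the microbiome denominator. Revision 16 extends the primary AMR analyses to 150, while the footnote to SAP Figure 1 still says that 60 contribute. This stands too, and is why both cases are worked above. Neither gives a sound rectal analysis.
- A missing-baseline indicator would keep every randomized community. That is reasonable for nasopharyngeal diversity, where the baseline subset is random, but the SAP does not specify it and it supplies nothing where no rectal baseline survives.
- A reader might infer that every rectal baseline was lost. Replacement by exactly 60 communities suggests it, but the protocol gives no number.
- A reader might also infer that the 24-month samples are wasted. They are not: the AMR outcomes use them in an ANOVA with no baseline term (SAP 3.5.2).

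**Conclusion.** The concern holds for the microbiome outcomes only. The stated diversity model cannot be fitted to at least 90 of the 150 resistance communities, and possibly to none of them for rectal swabs. If all 150 are meant to be analysed and the fit is complete-case, 60% of communities are lost for nasopharyngeal samples and 60% to 100% for rectal samples. With 60 retained, the standard error is up to 1.58 times larger, or about 1.28 to 1.46 times after the largest plausible gain from adjustment.

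These sizes rest on an even split of the 60 across arms and on resistance ICCs standing in for microbiome ICCs. The documents do not support saying that all microbiome analyses discard most or all communities: PERMANOVA and DESeq2 are affected only if a paired covariate is meant, and total rectal loss is unproven. The primary mortality and AMR analyses are untouched. The SAP should still be corrected, because following its stated model gives a less precise or infeasible analysis.

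**What to change.** In SAP 3.5.1, make the main analysis of all three microbiome outcomes the 24-month comparison by randomized arm, in all communities with 24-month microbiome data and without requiring a baseline value. This matches the AMR ANOVA in SAP 3.5.2 and is valid because the 150 communities were randomized 1:1:1 (Protocol 4.4.1).

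Keep baseline-adjusted models as a sensitivity analysis for nasopharyngeal samples in the communities with baseline data. State that the Round 4 rectal swabs are not a baseline covariate for the 150 communities, and say what they are for. State the number of communities and the unit of analysis for each sample type, and the form that baseline adjustment takes in PERMANOVA and DESeq2.

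The cost is SAP wording, plus the modest precision gain that adjustment would give within the 60 communities. On the figures above, that gain is outweighed by keeping all 150.
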